#### **7.5.4.5 Electrocardiograms**

12-lead ECGs are obtained at Weeks 52 and 104, and during Early Termination. ECG machines Mortara ELI 250c with VERITAS™ resting ECG interpretation algorithm will be provided to the sites.

Any ECG that is auto-interpreted as abnormal should be assessed for clinical significance by a health care professional with sufficient competence and experience of interpreting pediatric ECGs. If a patient shows an abnormal ECG, additional safety recordings may be made and the abnormality followed to resolution if required.

If the clinical situation allows, attempts should be made to have the 12-lead ECG recordings obtained after the patients have been resting in a supine position for at least 5 minutes. The patients should preferably avoid any postural changes during the ECG recordings and clinical staff will ensure patients are awake during the ECG recording.

Paper printouts of ECGs are to be stored as source documents to allow the possibility of retrospectively analyzing the ECGs. A study ECG manual will be provided.

Clinically significant ECG findings should be reported as AEs (see Section 7.5.4.1.1 for details).

#### **7.5.4.6 Other safety assessments**

##### **7.5.4.6.1 Physical examination and anthropometry**

The complete physical examination performed on Day 7 of Weeks 52 and 104, as well as during Early Termination, includes an assessment of the following: general appearance, skin (including potential reactions around the infusion site), eyes, ears, nose, neck, lymph nodes, throat, heart, lungs, abdomen, musculoskeletal system and extremities.

At Weeks 25 to 104, general appearance and skin at the infusion site are examined prior to start of each infusion and within 1 hour after end of infusion.

Height and head circumference are assessed at Weeks 52 and 104.

Weight is assessed every 4 weeks during the treatment period in order to determine the actual SOBI003 dose to be administered (Section 7.4.5). The body weight is obtained either on the day prior to the infusion or the day of infusion.

Height and head circumference are recorded in centimeters and weight in kilograms. For all weight assessments, a scale with at least 100-g accuracy should be used.

##### **7.5.4.6.2 Neurological examination**

At Weeks 52 and 104, and during Early Termination, a pediatric neurologist conducts an applicable age-related neurological examination including:

- Cranial Nerves
- Cerebellar function
- Sensory function
- Reflexes
- Motor function

Normal/abnormal status will be captured, and any abnormalities will be specified.

#### **7.5.4.7 Appropriateness of measurements**

The safety assessments in this study are widely used and generally recognized as reliable, accurate, and relevant.

#### **7.5.4.8 Data safety monitoring board**

A DMC is assigned to monitor safety and immunogenicity data. In addition, selected PD and efficacy data will be provided in order to facilitate a risk benefit review of study data. The primary responsibility of the DMC is to provide additional safety oversight of the study conduct in order to further protect study participants.

The DMC is planned to comprise an independent statistician and two clinicians that, collectively, have experience from DMC, management of pediatric patients with LSD, clinical immunology, and the conduct of clinical trials with ERT. The DMC members must not be investigators in the study or otherwise associated with the sponsor.

A DMC charter will specify the operating procedures including DMC membership, responsibilities, data review meeting details, and lines of communication with the study teams at Sobi and INC Research.

There are 2 scheduled DMC review meetings, one upon all patients' completion of Week 52 and one upon all patients' completion of Week 104.

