## STUDY DESIGN AND METHODS

Study design:

This is an open, single-arm, multicenter extension study to assess the safety, tolerability and efficacy of long-term SOBI003 treatment in pediatric MPS IIIA patients. The study is an extension of the First in Human (FIH) SOBI003-001 study, allowing continuous treatment of SOBI003 for up to 2 years. Study patients who complete Week 24 of the FIH study ([SOBI003-001](#)) will be invited to continue to Week 25 in the extension study.

As the phase I/II study has a sequential, ascending, multiple-dose design, the first patients will enter the extension study before finalization of the FIH study ([SOBI003-001](#)). When entering the extension study, these patients will receive

the highest dose that has been declared safe in the ongoing FIH study ([SOBI003-001](#)). Upon completion of the FIH study, an analysis aimed at selecting the dose for forthcoming studies will take place. Once the dose has been selected, this dose will be applied to all patients enrolled in the extension study.

SOBI003 is administered as weekly i.v. infusions over a period of time of 1 to 4 hours. Prior to initiation of each infusion, the patients are pretreated with a single dose of non-sedative antihistamine. If infusion-related reactions occur, then the infusion duration may be expanded up to 24 hours and supportive medication may be administered, at the discretion of the investigator.

The long-term safety, tolerability and immunogenicity of SOBI003 will be assessed throughout the extension study whereas measurements of clinical efficacy and disease-related biomarkers will be performed at Weeks 52 and 104. The potential of SOBI003 to improve the neurocognitive function will be compared to published data from a recent NH study.

The independent DMC employed in the FIH study ([SOBI003-001](#)) will continue to monitor safety and tolerability data in the SOBI003-002 study at pre-specified intervals.

The total duration of the extension study for an individual patient is 80 weeks, resulting in a total of 104 weeks (2 years) of SOBI003 treatment.

Number of subjects planned:

9-12

Diagnosis and main criteria for inclusion:

A patient must fulfill the following criteria in order to be included in the study:

1. Completion of study SOBI003-001
2. Informed consent obtained from the patient's legally authorized representative(s)

Assessments for safety and tolerability evaluation:

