#### **4.5 Data monitoring committee**

A data monitoring committee (DMC), independent from Sobi and Principal Investigators, is assigned to monitor all safety and immunogenicity data at intervals specified in Section 7.5.4.8. The primary responsibility of the DMC is to provide safety oversight of the study conduct in order to protect study participants.

The DMC employed in the FIH study ([SOBI003-001](#)) will continue to monitor safety and immunogenicity data in this extension study.

The DMC is planned to comprise an independent statistician and 2 clinicians that, collectively, have experience from DMC, management of pediatric patients with lysosomal storage disease (LSD), clinical immunology, and the conduct of clinical studies with enzyme replacement therapy (ERT).

A DMC charter will outline DMC membership, responsibilities, data review meeting details, and lines of communication with the study teams at Sobi and INC Research.

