## **7 Investigational plan**

### **7.1 Overall study design and plan**

This is an open, single-arm, multicenter extension study to assess the long-term safety, tolerability and efficacy of SOBI003 in pediatric MPS IIIA patients who previously participated in the FIH study ([SOBI003-001](#)) study. Patients completing the 24-week treatment of the FIH study will be offered to participate in the continuous 80 week treatment period of the extension study. The extension study starts with enrolment at Week 25, giving a total SOBI003

treatment duration of 104 weeks for each patient. Please refer to Figure 1 for an overview of the study design. A recent NH study is used as external control (22) to enable an evaluation of efficacy. Neurocognitive and adaptive behavior data assessed in the extension study at Week 52 and Week 104 following start of treatment will be compared to available NH data within the target study population. The NH population for comparison consists of 14 patients with a rapid progressive MPS IIIA disease and a baseline age of 12 to 72 months.

As the FIH study ([SOBI003-001](#)) has a sequential, ascending, multiple-dose design, the first patients will enter the extension study before the FIH study is completed. When entering the extension study, these patients will receive the highest dose that has been declared safe by the SRC in the ongoing FIH study ([SOBI003-001](#)) study. Patients enrolled in Cohort 1 of FIH study may thus be switched to the dose applied in Cohort 2 or Cohort 3, depending on safety clearance by the SRC. If a patient is initially switched to the dose applied in Cohort 2, the patient may subsequently later be switched to the dose applied in Cohort 3. Depending on recruitment rate in the FIH study ([SOBI003-001](#)) study, a patient enrolled in Cohort 1 may be directly switched to the dose applied in Cohort 3. Upon completion of the FIH study, an analysis aimed at selecting the dose for forthcoming studies will take place. Once the dose has been selected, this dose will be applied to all patients enrolled in the extension study.

[figure not shown]

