## **7.4 Treatments**

### **7.4.1 Treatments administered**

In this open-label study, the investigational medicinal product (IMP) is SOBI003.

SOBI003 is administered as i.v. infusions given once weekly for a duration of 80 weeks (from Week 25 until Week 104 following the first 24 weeks of IMP administration in the FIH study ([SOBI003-001](#)) study).

SOBI003 solution, 20 mg/mL, is mixed with NaCl 0.9% infusion solution prior to administration. For a bodyweight < 25 kg, the total infusion volume is 100 mL. For a bodyweight ≥ 25 kg, the total infusion volume is 250 mL.

Actual materials to be used for mixing SOBI003 solution with NaCl infusion solution (i.e., infusion solutions, syringes and needles) and for administering the infusions (i.e., infusion lines, syringes, manifolds, venous access ports) must be preapproved by Sobi to secure that all materials are compatible with SOBI003. Detailed IMP preparation instructions are provided in a separate IMP manual.

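### Both scheduled DMC reviews wait for the last patient: at least 28 of each child's 80 planned extension infusions (35%) come before the first review, and none remain at the second

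*Protocol*

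**What the plan says.** Protocol Section 7.5.4.8 fixes the schedule: "There are 2 scheduled DMC review meetings, one upon all patients' completion of Week 52 and one upon all patients' completion of Week 104". Section 4.5 says the committee "is assigned to monitor all safety and immunogenicity data at intervals specified in Section 7.5.4.8", so those two meetings are the full set of intervals. The synopsis mentions pre-specified intervals without adding any. No interim analysis is planned (Protocol Section 9.4.8, SAP Section 5.1).

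On purpose, Section 4.5 states: "The primary responsibility of the DMC is to provide safety oversight of the study conduct in order to protect study participants". Section 7.5.4.8 describes this oversight as additional to what is otherwise in place, and leaves meeting details and lines of communication to a charter.

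On dosing, Section 7.4.1 states: "SOBI003 is administered as i.v. infusions given once weekly for a duration of 80 weeks". This runs from Week 25 to Week 104, after 24 weeks in the first-in-human (FIH) study.

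On entry and dose changes, Section 7.1 says that "the first patients will enter the extension study before the FIH study is completed". At entry, those patients receive the highest dose that the safety review committee (SRC) has cleared in the FIH study. Further changes are foreseen: "If a patient is initially switched to the dose applied in Cohort 2, the patient may subsequently later be switched" to the Cohort 3 dose, or "a patient enrolled in Cohort 1 may be directly switched to the dose applied in Cohort 3". After the FIH study is complete, one selected dose is applied to everyone.

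**The concern.** Both triggers depend on the slowest patient. In a study with staggered entry, the first children are ahead of the last by the whole entry lag, so the first independent look at extension data comes later in their treatment than Week 52 suggests. None of the dose changes the protocol foresees is itself a trigger: not the switch at entry, not a later within-patient increase, not the move of all patients to the selected dose. The documented role of the SRC is clearing doses in the FIH study; neither document has it reviewing extension patients.

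This matters because long-term safety and tolerability is the primary objective (Section 6.1), and Section 5.2 accepts that severe and potentially life-threatening hypersensitivity may still occur. The protocol itself treats the period after a dose adjustment as one of higher risk, with 48-hour stays and hourly checks. Yet the independent committee is scheduled to look once while infusions continue and once after they have ended.

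**Working it through.** **Inputs**
- Review triggers: all patients complete Week 52; all patients complete Week 104 (Protocol 7.5.4.8).
- Extension dosing: weekly, Weeks 25 to 104 (7.4.1).
- Planned patients: 9 to 12 (synopsis).
- Entry lag L, the weeks between the first and last child's start: above zero by design (7.1), but no figure is given. It is treated below as an assumption and shown as a range.

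**1. The plan's own figure.** Extension infusions per child = 104 − 25 + 1 = 80, and 24 + 80 = 104. Both stated durations reproduce. The planned total is 80 × 9 = 720 to 80 × 12 = 960.

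**2. First review, the minimum that holds at any accrual.** When the last child completes Week 52, that child has had 52 − 24 = 28 planned extension infusions, and 28/80 = 35%. All other children have had at least as many. The pooled minimum is 28 × 9 = 252 to 28 × 12 = 336 infusions. The last child then has 104 − 52 = 52 left.

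**3. Dose switches relative to the first review.** The entry switch is at Week 25, so it comes 52 − 25 = 27 weeks before Week 52 even for the last child. The common dose follows completion of the FIH study. If the last child to finish that study at Week 24 also enters the extension, the first review is at least 52 − 24 = 28 weeks later. Unless dose selection takes longer than that, the switch of all patients also comes first.

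**4. First review, the first child.** That child is at Week 52 + L and has had min(80, 28 + L) infusions.

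| L (weeks, assumed) | First child at | Given | Left |
|---|---|---|---|
| 0 | Week 52 | 28/80 (35%) | 52 |
| 24 | Week 76 | 52/80 (65%) | 28 |
| 26 | Week 78 | 54/80 (67.5%) | 26 |
| 39 | Week 91 | 67/80 (84%) | 13 |
| 48 | Week 100 | 76/80 (95%) | 4 |
| 52 or more | Week 104 or finished | 80/80 (100%) | 0 |

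**5. First review, all children pooled.** With even entry and L up to 52, the mean per child is 28 + L/2.
- L = 0: 28/80 = 35%.
- L = 26: 41/80 = 51%.
- L = 52: 54/80 = 67.5%, about 68%.

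**6. Second review.** Every child has completed Week 104, so 80 − 80 = 0 infusions remain in this study, whatever L is.

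These counts are planned infusions; missed doses or withdrawals lower them. Time for data cleaning and convening the meeting pushes the reviews later.

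**The case against.** The strongest reply is that the DMC is not the main safety mechanism. The study is open-label and single-arm, so investigators and sponsor see events as they occur. Serious adverse events are reported within 24 hours, with separate notice to the sponsor's medical director (7.5.4.1.4). The same section provides for prompt notification of investigators and authorities about safety findings. Investigators can withdraw a child from treatment (7.3.3.1). Entry doses have already been cleared by the SRC, and a dose adjustment brings 48-hour stays, hourly checks during infusion, continuous oximetry and safety laboratory tests for three infusions, with some relaxation for decreases made without safety concerns (Table 1, 7.5.1.7.1, 7.5.4.4). Section 7.5.4.8 limits only scheduled meetings; the charter may allow others. The same committee also served the FIH study, which overlaps with early extension dosing, and its schedule there is not in these documents.

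All of this stands, and it lowers the severity. It does not supply a scheduled independent look at extension data before the last child completes Week 52, and no passage routes these reports to the DMC between meetings.

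Three stronger readings are tempting but not supported:
- **The first children will be near or past their last dose at the first review.** That needs a lag of roughly 40 to 52 weeks or more, and the documents give no lag. At 26 weeks the first child still has 26 infusions left.
- **A signal in the early children could not reach the DMC in time to protect later ones.** The last child has 52 infusions left at the first review, and whether the DMC hears of events between meetings is not stated either way.
- **The second review has no value.** Section 7.1 allows a follow-on study starting directly afterwards, which that review could inform.

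**Conclusion.** The point holds as a weakness in the timing of scheduled independent oversight. Three results need no accrual assumption: at least 28 of 80 planned infusions per child (35%) precede the first review; every entry dose switch precedes it; and none of this study's infusions remain at the second. The 51% and 68% figures are conditional on lags of 26 and 52 weeks with even entry, and should be cited only as such.

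No endpoint or analysis is invalidated and no passage is contradicted. Other safety channels operate throughout, and the unseen charter may already cover part of the gap. The appropriate grade is a recommended, low-cost improvement rather than a required correction.

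**What to change.** In Section 7.5.4.8 and the DMC charter:
1. Replace the all-patients triggers with periodic reviews of cumulative data, counted from the first patient's Week 25 and continuing while any patient is dosed, for example every 6 months.
2. Add a DMC data review once the first patients have completed the intensified schedule (Table 8) after a dose increase, and another after all patients have moved to the selected dose.
3. State a trigger for ad hoc meetings and how safety reports reach the DMC between meetings.
4. State the expected entry lag.
5. Keep the Week 104 meeting as a close-out review.

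Taking 6 months as 26 weeks, the first periodic review would come after the first child's 26th extension infusion (26/80 = 32.5%), whatever the lag. Under the present rule that child would have had 28 at L = 0, 54 at L = 26 and 80 at L = 52. The gain in timing is therefore small without a lag and grows with it. Dosing spans 80 + L weeks, so periodic reviews during dosing would number 80/26, about 3, at L = 0 and 132/26, about 5, at L = 52, against one now if any child is still being dosed at that point.

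The cost is protocol and charter wording plus a few more data cuts and meetings for an existing three-member committee. No patients, visits or samples are added, and no dose or treatment rule changes.

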## **7.5.5 Pharmacokinetic assessments**

### **7.5.5.1 Sampling procedures**

The sampling procedures are briefly described below and are described in more detail in the Study laboratory manual. Blood samples are obtained through the central venous access port to characterize SOBI003 PK in serum. For the PK samples collected at the end of infusion a PK sample will also be collected from a peripheral venous line, as described in more details below. A blood volume of 0.3 mL will be collected from the central venous access port and an additional 0.3 mL blood will be collected from the peripheral venous line, as applicable.

PK blood samples will be collected before start of infusion, at the end of infusion and 168h after start of infusion at Weeks 38, 52, 78 and 104.

If the dose is adjusted in a patient, PK blood samples will also be collected before, at the end of infusion and 168 h after start of the infusion for the adjusted dose. In addition, PK blood samples will be collected before, at the end of infusion and 168 h after start of the infusion 4 weeks and 8 weeks after adjusting the dose. A PK blood sample will also be collected before the 3rd adjusted dose, as reference for ADA (see Section 7.5.4.3 for more details).

Acceptable deviations from these planned sampling time points are the following: 4 h (end of infusion) (+0.5h), and 168h (- 1h).

Details on PK blood sampling are presented in Section 7.5.1.1. and summarized in Table 10.

Duplicate aliquots are required for each sampling time point. Separate blood samples from a peripheral venous line are collected in parallel for samples collected at the end of infusion in order to compare serum SOBI003 concentrations in samples collected from a peripheral line with samples from the central venous access port line, which is used also for the i.v. administration of SOBI003. The purpose of these parallel samples is to confirm that the SOBI003 i.v. infusion does not interfere with the blood sampling. The PK samples from a peripheral venous line for the End of infusion sample can be excluded if it has been confirmed in the FIH study (SOBI003-001) that the SOBI003 i.v. infusion does not interfere with the PK blood sampling.

In addition, at each time point a sample is collected for immunogenicity, a blood sample is obtained for determination of SOBI003 in serum. In case of a time deviation for the immunogenicity sample, the time for the PK sample should be adjusted accordingly, or an additional PK sample may have to be collected. Therefore, in case the SOBI003 treatment is terminated prior to Week 104, then a PK and immunogenicity sample should be obtained as soon as possible after the decision of early treatment termination, as well as 30 to 40 days after the final SOBI003 infusion.

For patients with confirmed ADA levels, blood samples for PK and immunogenicity analysis should continue in accordance with Section 7.5.4.3.

CSF samples (0.5 mL) are collected during general anesthesia at Day 2 on Weeks 52 and 104 for determination of SOBI003. Triplicate aliquots are required for each sampling time point. At the time of CSF sample collection, a blood sample will also be collected for determination

of SOBI003 in serum. In case the time point for the CSF sample is deviating from the planned time point, the blood samples should be adjusted accordingly.

The exact time of the SOBI003 infusion start and completion as well as of each PK sampling are recorded in the CRF for each patient.

Sampling, storage and shipment details are provided separately in the Study laboratory manual.

#### **7.5.5.2 Bioanalytical method**

SOBI003 concentrations in serum and CSF are determined at a central laboratory (York Bioanalytical Solutions Limited, [name]) by the use of a validated immunoassay. The bioanalytical method may not be specific for SOBI003 and may cross-react with endogenous sulphamidase. Potential endogenous pre-dose sulphamidase concentrations are taken into consideration in the PK analysis e.g. by subtracting these levels from post-dose SOBI003 concentrations

#### **7.5.5.3 Non-compartmental pharmacokinetic analysis**

PK calculations, based on serum concentrations, are performed in Phoenix WinNonlin by means of NCA. Individual serum concentration data from each patient and the exact time points for blood sampling will be used throughout the analyses. The following multiple-dose PK parameters will be determined for SOBI003 at Weeks 39, 52, 78 and 104, and during dose-adjustments:

- The time of the end of the infusion of SOBI003,  $t_{\text{End of inf}}$
- The observed serum concentration at the end of infusion of SOBI003,  $C_{\text{End of inf}}$
- The observed serum concentration immediately before the start of infusion of SOBI003,  $C_{\text{Pre-dose}}$
- The area under the plasma concentration-time curve from time 0 to last sample,  $AUC_{168h}$  Clearance, CL

The area under the plasma concentration-time curve from time 0 to last sample,  $AUC_{168h}$  calculated according to the linear log trapezoidal method. Other PK parameters may be calculated as applicable.

